Anxiety and Depressive symptoms: The Hopkins Symptom Checklist-25 (HSCL-25)² will be used to measure anxiety and depressive symptoms experienced over the past month at baseline, post-intervention, and three-month post-intervention. It is composed of a 10-item subscale for anxiety and a 15-item subscale for depression, with each item scored on a Likert scale from 1 (not at all) to 4 (extremely).

Secondary outcome

Physiological stress: Cortisol hair-test (average hormone levels over the past three months) will be used as a biomarker to measure physiological stress. Neuroendocrine indicators, such as cortisol, are effective stress biomarkers because they are the first to respond to a given stressor and coordinate the physiological response of other bio-physiological systems.

Interventions and Duration

Study Arms:

Experimental: Problem Management Plus for Immigrants (PMP-I) at family settings

Active Comparator: Talk program with Community Support Service Pamphlet (CSS)

Assessment:

Baseline, Post-Intervention, and 3-month Post-Intervention

Intervention:

PMP-I is a 5-week, peer-led, culturally tailored psychoeducation, behavioral activation, and problem-solving (90 minutes), breathing and yoga intervention (90 minutes) in a family setting. PMP-I will use a structured approach, including once a week, face-to-face sessions, breathing, yoga practice, homework that includes recording activities, rebuilding individual skills, or learning new skills to reduce stress.

- 1. Managing Stress:** Breathing and yoga practices, stress-management sessions, and behavioral activation exercises to strengthen positive coping strategies.
- 2. Managing Problems:** Practice exercises to identify the problems, develop solutions, and plan a strategy to carry out those solutions.
- 3. Behavior Activation:** Communication skill sessions and practice exercises to identify and carry out pleasant tasks.
- 4. Strengthening Social Support:** Social skills session and practice exercise to identify social support.
- 5. Staying Well:** Make a plan that helps to create a supportive family environment.

Sample Size and Population

This study will be conducted among 226 Bhutanese adults settled in Massachusetts.

STUDY TEAM ROSTER

Principal Investigator: [name]., MPH, MPHC, CGM
Assistant Professor, College of Nursing, [name], University Massachusetts Amherst, MA, 01003
Email: [contact]
[contact]

Co-Investigator: [name].

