3 STUDY DESIGN

Study design: This mixed-methods study will incorporate a two-arm randomized controlled feasibility trial and qualitative evaluation of the acceptability of Problem Management Plus for Immigrants (PMP-I) intervention to a range of stakeholders.

Allocation: Randomized

Intervention Model: Parallel Assignment

Masking: None

Primary purpose: Prevention

Outcome Measures

[figure not shown]
Name: Anxiety & Depressive Symptoms

Type: Primary

Time Frame: Baseline, Post-intervention, 3-month Post-intervention

Brief Description: The Hopkins Symptom

Checklist-25 (HSCL-25)² will be used to measure anxiety and depressive symptoms experienced over the past month. It is composed of a 10-item subscale for anxiety and a 15-item subscale for depression, with each item scored on a Likert scale from 1 (not at all) to 4 (extremely). The scale was validated for use in Nepal with a clinical DSM-IV diagnosis of major depressive disorder. The sensitivity and specificity with a cutoff point

of 1.75 were 0.87 and 0.60, respectively, with an area under the curve of 0.79.⁵⁰ The HSCL-25 has widely been used in studies among refugees in other countries as well as Nepal. The HSCL-25 score was categorized into two groups: the cutoff score of 1.75; depressed (1.75 or more), and not depressed (below 1.75). The scale has high internal consistency for anxiety (Cronbach's $\alpha = 0.92$) and depression (Cronbach's $\alpha = 0.94$) in our previous study with the same population group.³⁹

Name: Perceived Stress

Type: Primary

Time Frame: Baseline, Post-intervention, 3-month Post-intervention

Brief Description: The 10-item Cohen Perceived Stress Scale (PSS)¹ will assess perceived stress. The PSS uses a 5-point Likert scale (ranging from 0, “never” to 4, “very often”) to assess psychological stress experienced during the past month, including the extent to which situations felt unpredictable, uncomfortable, and overwhelming. The items included in the PSS scale are easy to understand as it was designed for use with community samples with junior high school education. This scale has been widely used in diverse populations, including immigrants. The scale has high internal consistency (Cronbach's $\alpha = 0.80$) in our previous study with the same population group.³⁹ Items were summed to provide a total score with higher scores indicating greater perceived stress.

Name: Physiological stress

Type: Secondary

Time Frame: Baseline, 3-month Post-intervention

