9 STATISTICAL CONSIDERATIONS

9.1 Sample Size and Randomization

The pilot project aims to estimate the magnitude of the difference between the preventive intervention and the education control on the primary outcomes of interest (stress, anxiety, depressive symptoms) to inform the design of a large-scale intervention. A study comparing PMP to a treatment-as-usual control in Pakistan⁶¹ found a mean difference of about 7 points with a standard deviation of 8.5 on a measure of anxiety and depression for effect size ($ES=.86$). We do not expect our ES to be as large as what was observed in the Pakistani study⁶¹ given that we are doing a prevention trial and not an intervention study in a distressed population so that this study will provide an estimate of the ES of PMP as a preventive intervention.

We conducted a power analysis to detect an ES as small as $ES=.30$ with $\alpha = .05$ and power of $.80$. We may find a larger effect in our pilot, but our understanding is that power estimates should be based on the smallest effect that we want to detect rather than the size of the effect that we expect.⁶² We expect that families will average approximately 2-4 adult persons based on our pilot data, and conducted our power analysis to account for the correlation among family members. Analyses were conducted using Optimal Design,⁶³ which is power analysis software created for cluster randomized trials such as the present study. Accounting for the intra-correlation among family members of $.10$ and $\alpha = .05$, we would have 80% power to detect a standardized difference of $ES=.30$ between two treatment groups of 116 families (58 per treatment arm) with an equal probability of being randomized to each of our two intervention arms.

As noted above, we do not expect our ES to be as large as in the Pakistani study, but a sample of that size should be sufficient to provide the estimates of the differences between the conditions (with standard deviation in our sample) and the correlations between the targets specified by theory and our primary outcome of interest to inform the design of a larger-scale controlled trial. The other goal for the project is to determine whether the intervention affects the target mechanisms specified by theory to mediate or moderate the intervention's impact on the outcomes. Those estimates we will get from the correlation between our respective targets (coping and self-efficacy) and the primary outcomes.

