Figure 1 provides a visual representation of our proposed analyses, in which treatment is a predictor of treatment targets or mechanisms (i.e. the mediators such as coping), which are in turn associated with outcomes. As reviewers 1 and 3 note, in mediational analyses, variables must be measured in *temporal sequence*.

Figure 2 provides a visual representation of our proposed temporal sequence of variable measurement for mediational analyses, in which treatment randomization occurs before mediator target measurement, which in turn are collected before the outcome measure used in the proposed analyses. Second, it is crucial to test the *indirect effect* (a*b paths) of the treatment on the outcome through the hypothesized mediators. As the indirect

effect is not normally distributed, we will assess its significance via Monte Carlo simulated confidence intervals, which are the recommended counterpart in multilevel mediation to bootstrapped confidence intervals used in single-level analyses.⁶⁶⁻⁶⁸

Each potential mediational sequence will be tested in this manner (see **Table 1** for mediators and outcomes to be tested). While we acknowledge that mediational analyses are difficult to adequately power in a sample of our proposed size,⁶⁷ we believe these preliminary analyses will help identify potential mechanisms for our treatment effect. If baseline differences in treatment groups are found in either the mediating or outcome variables, baseline measures will be controlled for in all analyses. Sample mixed-format multilevel equations are provided below, where the nesting of measures (i) within families (j) is accounted for by the random effects u_{0js} : γ_{01} in the Mediator equation is the ‘a path’, and γ_{10} in the Outcome equation is the ‘b path.’

Table 1 Mediators and Outcome Variables

Mediators (Targets)	Outcomes
Coping, Self-Efficacy	Perceived Stress
Family or Social Support	Physiological Stress
Family Conflict Resolution	Anxiety Symptoms
Family Satisfaction	Depressive Symptoms
Family or Social Network	

$$T2Mediator_{ij} = \gamma_{00_Med} + \gamma_{01_Med} * TreatmentCondition_j + u_{0j_Med} + r_{ij_Med}$$

$$T3Outcome_{ij} = \gamma_{00_Out} + \gamma_{10_Out} * T2Mediator_{ij} + \gamma_{01_Out} * TreatmentCondition_j + u_{0j_Out} + r_{ij_Out}$$

The key estimates are the association of the treatment condition with the mediator (γ_{01_Med} , a path) and the association of the T2 mediator with the T3 Outcome (γ_{10_Out} , b path).

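### Aim 2c omits the outcome measured at the same Day 42 visit as the mediator, so a target that only followed the drop in stress can test positive; a sensitivity analysis and a reverse model are needed

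*Combined protocol and SAP*

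**What the plan says.** The combined protocol and SAP, Section 9.2 (Aim 2c), accepts that mediation needs variables in time order, and describes its sequence so: "treatment randomization occurs before mediator target measurement, which in turn are collected before the outcome measure used in the proposed analyses". The printed outcome equation regresses the T3 outcome on the T2 mediator and the arm, with a family random effect and a residual. The b path is "the association of the T2 mediator with the T3 Outcome". It is multiplied by the a path (arm to T2 mediator), and the product is tested with a Monte Carlo confidence interval. Baseline values enter only if the arms are found to differ at baseline. The analyses are called preliminary and hard to power, and are meant to point to possible mechanisms.

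For both primary outcomes Section 3 gives "Time Frame: Baseline, Post-intervention, 3-month Post-intervention". Sections 6.1 and 6.2.3 place these assessments at Day 42, the visit that supplies the T2 coping, self-efficacy and family conflict resolution scores. Hair cortisol is taken at baseline and the final visit only. The T2 outcome appears nowhere in the Aim 2c text or equations, and no reverse-order model or sensitivity analysis is given. Figure 2, which illustrates the sequence, is not in the text available, so this point rests on the wording and equations.

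**The concern.** Placing the outcome at T3 orders the mediator against the T3 reading. It does not order the mediator against the change in the outcome that had already happened by T2. Suppose PMP-I lowers stress by Day 42, people who feel less stressed rate their coping higher that day, and stress on Day 42 carries through to Day 132. The arm then predicts T2 coping, and T2 coping predicts T3 stress, although coping had no effect on stress. Baseline adjustment cannot block this route, because the T2 outcome changes after randomization.

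The protocol makes the route plausible. Half of each 180-minute session is yoga and breathing (Section 5.1), which the same section credits with stress reduction in the pilot programs. PSS and HSCL-25 look back one month, so a Day 42 score reaches back to about Day 12 and spans most of the sessions (Days 7 to 35).

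At stake is what Aim 2c can tell the larger trial. Section 9.1 makes the effect on target mechanisms a project goal and wants target-outcome correlations for planning. The stated model cannot separate coping that lowers stress from lower stress that improves coping.

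**Working it through.** **Inputs from the documents.** 116 families, 58 per arm; intra-family correlation .10; alpha .05; effect size .30 (Section 9.1). Family size: "We expect that families will average approximately 2-4 adult persons based on our pilot data". The synopsis says: "This study will be conducted among 226 Bhutanese adults settled in Massachusetts", which is 226/116 = 1.95 per family. PSS internal consistency .80 (Section 6.2.2). The effect of .86 that Section 9.1 cites from a distressed population is used only as an upper bound.

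**The plan's own figure.** The 80% power belongs to Aim 2b; no power or error rate is stated for Aim 2c. With m adults per family, effective n per arm = 58m/(1 + .10(m − 1)), and power = Φ(.30·√(n/2) − 1.96).
- m = 4: n = 232/1.3 = 178.5; Φ(2.834 − 1.96) = .81.
- m = 3: n = 174/1.2 = 145; Φ(2.554 − 1.96) = .72.
- m = 2: n = 116/1.1 = 105.5; Φ(2.178 − 1.96) = .59.

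The 80% is reproduced two-sided at 4 adults per family. That is a separate matter; it serves here to fix the effect size and family sizes.

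**Why an inert target tests positive.** Let A be the arm, Y the outcome and M the target, in SD units:
- Y2 = −d·A + .5·Y1 + error
- M2 = −k·Y2 + other terms
- Y3 = .6·Y2 + .2·Y1 + error, with no M2 term

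The values .5, .6, .2 and k = .3 or .5 are assumptions. The a path is k·d: at d = .30 it is .09 (k = .3) or .15 (k = .5). With Y2 left out, and ignoring the family term, the fitted b path is −.6·k·Var(Y2 | A, baseline)/Var(M2 | A, baseline). This is non-zero although M has no effect.

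**Simulation.** 1,000 trials per setting, random-intercept maximum likelihood, 95% Monte Carlo interval for a*b. Entries are the percentage of trials in which the interval excludes zero:

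| Adults per family | d | k | As printed | Baseline M and Y always adjusted | Plus T2 outcome |
|---|---|---|---|---|---|
| 2 | .30 | .3 | 10.4 | 8.6 | 0.1 |
| 2 | .30 | .5 | 19.8 | 23.3 | 0.8 |
| 2 | .50 | .3 | 23.4 | 22.1 | 1.1 |
| 2 | .50 | .5 | 47.3 | 56.4 | 2.5 |
| 2 | .86 | .3 | 56.4 | 55.4 | 3.0 |
| 2 | .86 | .5 | 88.8 | 93.8 | 4.9 |
| 4 | .30 | .3 | 16.5 | 18.1 | 0.5 |
| 4 | .30 | .5 | 32.2 | 38.2 | 1.3 |

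A separate simulation (600 trials per cell, least squares with family-clustered errors, baseline adjusted) gave 7-23% at d = .30 with 232 adults and 12-39% with 464. A further run with 2 adults per family gave 11-27% at d = .30 and 20-56% at d = .50. Together these give 7-27% (about 2 adults per family) and 12-39% (4 adults) at d = .30.

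With baseline adjusted, the b path alone was falsely significant in 84-100% of trials. What limits the false-mediator rate is the weak a path. At d = .30 with 2 adults per family it was detected in 11.6% and 24.3% of trials, and the target tested as a mediator in 8.6/11.6 = 74% and 23.3/24.3 = 96% as many. In the same cells the mean spurious a*b was −.019 and −.044, against a total effect of −.6 × .30 = −.18, that is 11% and 24%.

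**Limits of adding the T2 outcome.**
- Measurement error: with outcome reliability .80, k = .5 and 2 adults per family, the false rate stays at 4.6% (d = .30) and 25.5% (d = .86).
- A true mediator that has acted by Day 42: let treatment move the target by .30, the target move Y2 with slope .5, and Y2 persist at .6. Detection falls from 72% to 3%.
- A target that keeps acting after Day 42: detection with the T2 outcome included was 49-95%.
- A reverse model that leaves out the T2 mediator was positive in 25-78% of runs when the target truly was the cause.

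**The case against.** The plan is cautious. It treats time order as a requirement and does not say that the order proves direction. Its equations are offered as samples, it calls both paths associations, and it labels the work preliminary. At the planned effect and about 2 adults per family, the low end of the false rate (7-9%) is little above 5%, and the slopes behind it are not in the documents. Conditioning on the T2 outcome also has a price: that value lies on the plan's own proposed path from treatment through coping to stress, so a true early mediator looks no better than an inert one.

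Much of this stands. A reader might infer that an inert target will be declared a mediator as a matter of course, or that the plan claims its lag settles direction. The documents support neither: the error is a rate, and the plan's wording is associational. A reader might also infer that the T2-adjusted model should replace the stated one, or decide which targets count. The 72% to 3% loss rules that out.

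What remains is that a*b is tested for significance to identify mechanisms, an outcome reading that bears on direction is collected and unused, and low power is no answer to a bias that grows with sample size and with a successful intervention.

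**Conclusion.** The gap is real and cheap to close. For PSS and HSCL-25, the Aim 2c model can return a significant indirect effect for a target that merely followed an earlier fall in the outcome, and baseline adjustment does not prevent it. At d = .30 the rate is roughly 7-27% with about 2 adults per family and 12-39% with 4, rising with the effect. The sizes rest on the assumed slopes (.3 to .5) and persistence (.6). The existence of the bias needs only that all three links are non-zero.

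The near-zero rates with the T2 outcome added assume error-free measurement, so that model is a sensitivity analysis and not a cure. The point does not show that any target is inert, and it does not touch Aim 2b.

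**What to change.** For PSS and HSCL-25 only:

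- Keep the stated model. Add a pre-specified sensitivity analysis with the T2 outcome and the baseline mediator and outcome in the T3 outcome equation.
- Add the reverse model: T3 mediator on T2 outcome, T2 mediator, baseline values and arm, for targets measured at both T2 and T3.
- Report the indirect effect with and without the T2 outcome. If it excludes zero only without it, report an association with direction unresolved, neither confirming nor rejecting the target as a mediator.
- For hair cortisol, state that direction cannot be examined, because there is no T2 sample.
- Reconcile the Section 6.1 schedule with Section 10.1.3. The schedule, as it reads in the text, marks family satisfaction at baseline only and has no row for social support or social network. Section 10.1.3 lists all three at every time point, and Table 1 names them as mediators.

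The cost is one sensitivity model, one reverse model and a sentence on interpretation. PSS and HSCL-25 need no new visit or measurement. The downside should be stated in the plan: the adjusted model has almost no power for a true mediator whose effect was complete by Day 42, and at a PSS reliability near .80 it leaves some bias.

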Where the outcome is measured at each repeated measure *i* for each individual *j* within each family *k*. Time is centered at the endpoint, so that β_{00k} estimates the value of the outcome for each family at the end of the study, informed by all data points available for that family. If an endpoint observation is missing due to drop out, the advantage of multilevel modeling is that it utilizes maximum likelihood estimation, which estimates the expected outcome for that cluster using information from prior assessments as well as the expected value from the entire model. The key test of difference in the outcome between the treatment groups is represented by γ_{001} (in bold); this is a test of difference in outcome at endpoint between families randomized to PMP versus not. We expect this test of difference to be statistically significant based on our power analysis for the difference in outcome *level* at the endpoint. Note that this model will also test group differences in *change* in each outcome (γ_{101}). While our pilot is not powered for the significance of effects of change over time, we will be able to obtain estimates of ES for change for use in future larger-scale trials and analyses.

The ultimate goal of our analyses is to estimate the ES for this prevention trial for each outcome, to inform our planning of a full-scale trial. As noted earlier, we have powered this pilot prevention trial with a conservative estimate of effect size based on a similar study in a clinical population, but no known studies have characterized the precise effect size of PMP as a preventive intervention; a goal of our pilot is to estimate the expected effect on the population of interest (i.e. an at-risk vs clinical population). All analyses will be performed using SAS, version 9 (SAS Institute Inc, Cary, NC).

Aim 2c Mediating effects: Separate models will be created to evaluate the relationships between mediators (targets) and outcomes and to explore mediators (e.g. coping) of intervention-outcome relation.

In this aim, we aim to test the potential *mediators* of the treatment-outcome association by conducting mediational analyses in a multilevel regression framework.⁶⁵ Following current

[figure not shown]
Figure 1 Mediational Analysis Framework

recommended best practices in mediational analysis, we will conduct these analyses using recommended practices for mediation with a multilevel framework.⁶⁶⁻⁶⁸

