Multiplied together, these coefficients form the indirect effect of the treatment on the outcome and are tested for significance via Monte Carlo simulated confidence intervals. All analyses will be performed using Mplus, version 8.⁶⁹

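### Aim 2c tests each target in its own single-mediator model, so an inert target that PMP-I moves, and that correlates within arms with a working target, is declared a mediator far more often than 5% of the time

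*Combined protocol and SAP*

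**What the plan says.** Section 9.2, Aim 2c, sets out the mediation analysis target by target: "Separate models will be created to evaluate the relationships between mediators (targets) and outcomes". The sample outcome equation is "T3Outcome_{ij} = \gamma_{00_Out} + \gamma_{10_Out} * T2Mediator_{ij} + \gamma_{01_Out} * TreatmentCondition_j" plus error terms, so it holds one target measured at T2, the treatment arm and a family random effect. Then: "Each potential mediational sequence will be tested in this manner". The product of the two paths, a*b, is the indirect effect, and the products "are tested for significance via Monte Carlo simulated confidence intervals". The interval level is not stated; 95% is assumed here.

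Table 1 lists at least six targets, counting coping and self-efficacy separately, against four outcomes. That is at least 6 × 4 = 24 sequences.

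Baseline values enter only conditionally: "If baseline differences in treatment groups are found in either the mediating or outcome variables, baseline measures will be controlled for in all analyses".

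On status, the section concedes weak power ("While we acknowledge that mediational analyses are difficult to adequately power in a sample of our proposed size") but still expects a substantive product: "we believe these preliminary analyses will help identify potential mechanisms for our treatment effect". Section 9.1 also names the target mechanisms as a project goal. The document describes no model with several targets, no adjustment for other targets and no sensitivity analysis for this aim.

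**The concern.** The question is whether PMP-I acts on stress, anxiety or depression through a given target. A one-target equation asks something weaker: does treatment shift this target, and does this target track the later outcome within arms when all other targets are ignored? The two questions differ when targets are correlated, and Table 1 invites correlation. It pairs coping with coping self-efficacy, support with network, and family conflict resolution with family satisfaction. The intervention components in section 5.1 aim at several of these domains together.

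At stake is what the pilot passes to the larger trial. If one target works and its neighbours do not, Aim 2c may list several as potential mechanisms and offer no way to tell them apart. Baseline adjustment does not address this, because the omitted variable is another post-treatment target.

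**Working it through.** **Step 1. The plan's own figure.** There is no power or error figure for Aim 2c. Section 9.1 gives 80% power for ES = .30 on the primary comparison (116 families, 58 per arm, intra-family correlation .10, alpha .05, taken as two-sided). With m adults per family, effective n per arm = 58m / (1 + (m − 1) × .10) and power = Φ(.30 × √(n/2) − 1.96).

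- m = 2: n = 116/1.10 = 105.5, power .586
- m = 3: n = 174/1.20 = 145, power .724
- m = 4: n = 232/1.30 = 178.5, power .809

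The stated 80% is reproduced at 4 adults per family, the top of the plan's range of 2-4. The synopsis total of 226 adults is 226/116 = 1.95 per family, so m = 2 (232 adults) is the closest whole number. A .3 SD shift in a target is the same test as this comparison, so .586 is also the chance that its a path is significant at m = 2.

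**Step 2. Algebra.** Let target 1 affect the outcome with slope b, let target 2 have no effect, and let their within-arm correlation be r (standardised scales). Regressing the outcome on target 2 and treatment gives, in large samples, a slope of b × r rather than 0. With b = .4 this is .12, .20 and .28 at r = .3, .5 and .7. At a shift of .3 and r = .5, the apparent indirect effect of the inert target is .3 × .20 = .06. The true value is 0.

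**Step 3. Rough check.** The interval for a*b excludes zero roughly when both paths are significant. In simulation at m = 2 and b = .4, the inert target's b path is significant in 44.1%, 86.2% and 99.3% of trials at r = .3, .5 and .7. The products are:

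- .586 × .441 = .26
- .586 × .862 = .51
- .586 × .993 = .58

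**Step 4. Simulation.** 116 families, intra-family correlation .10, 1,500 trials per setting, random-intercept fits, 95% Monte Carlo interval. *Assumed, because the documents give no values:* both targets shifted by .3 SD, b = .4, no dropout. Percentage of trials in which the inert target is declared a mediator:

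| Adults per family | r = 0 | r = .3 | r = .5 | r = .7 |
|---|---|---|---|---|
| 2, plan's model | 2.8 | 22 | 48 | 59 |
| 3, plan's model | 3.9 | 44 | 72 | 75 |
| 4, plan's model | 4.1 | 59 | 81 | 81 |
| 2, both targets in the model | 2.7 | 2.4 | 2.9 | 2.3 |

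Repeat simulations at 232 adults gave up to 25%, 50% and 59% at r = .3, .5 and .7.

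**Step 5. Range.**

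- b = .2, shift .3, r = .5, 232 adults: about 15-18%.
- Shift .2, b = .3, r = .5: 14%, 30% and 39% at 2, 3 and 4 adults per family.
- Shift .5, b = .5, r = .7: 96% to 99.7%.
- Across all settings in which PMP-I moves the inert target, the joint model gives 1-6%.

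**Step 6. What PMP-I must move.** If it shifts only the inert target (working target 0, inert .3, b = .4, r = .5), the rates are 49%, 68% and 81% at 2, 3 and 4 adults. If it does not shift the inert target, they are 3-5%.

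**Step 7. Cost to a real mediator.** At 232 adults, shift .3, b = .4 and r = .5, the working target is detected in 57% of trials in both models. At b = .2 and r = .5 with two targets, detection falls from about 47% to 40%.

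**The case against.** The strongest reply is that this is an exploratory aim in a pilot. The equations are labelled as samples, the analyses are called preliminary, low power is admitted, and no rule promotes or drops a target on a significant interval. That is fair and limits how serious the point is. It does not answer it. Low power warns of missed mediators, whereas this error produces false ones, and it grows with sample size (48%, 72%, 81% at r = .5).

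A second reply concerns the remedy. If targets act in sequence, a joint model hides the upstream one. In a simulated chain from treatment to self-efficacy to coping to outcome (232 adults, shift .3, link .5-.7, b = .4), the single-mediator model finds the upstream target in about 49-59% of trials and the joint model in about 2-3%. All targets are measured at the same T2 visit, so the data cannot say which structure holds. This stands, and it rules out naming mechanisms from the joint model alone.

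A third reply is that the number of targets is unsettled. The schedule in section 6.1 shows a Day 42 measure for coping, self-efficacy and family conflict resolution only, while section 10.1.3 lists social support, social networking and family satisfaction at all three assessments. This also stands, so no figure for the number of falsely flagged targets is offered here.

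**Conclusion.** The point holds as an inexpensive improvement to the plan. As specified, a significant single-mediator indirect effect does not show that the effect runs through that target. Near the stated sample of 226 adults, with a .3 SD shift and b = .4, an inert target is flagged in roughly 22-59% of trials for correlations of .3 to .7, and in about 15-18% at b = .2 and r = .5. The joint model gives about 2-3%. Every shift, slope and correlation here is an assumption.

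A reader might infer that an inert target is declared a mediator whenever it correlates with a working one. The documents do not support that. The bias is certain only in large samples, and at 232 adults with a .3 shift the a path alone caps the rate near 59%. A reader might also infer that PMP-I has to move both targets. It need move only the inert one, and the correlation that matters is within arms. Nor do the documents say that Aim 2c exists to pick the single target that carries the effect. They speak of exploring mediators and of potential mechanisms.

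**What to change.** In section 9.2, Aim 2c:

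- Keep the single-mediator models.
- For each outcome, add one joint (parallel-mediator) model in Mplus, already the plan's software for this aim. Regress the T3 outcome on treatment and all Table 1 targets that have T2 data, with the same family random effect.
- Compute each target's specific indirect effect (its a path times its b path from the joint model) with a Monte Carlo interval, and report it beside the single-mediator result.
- State that a single-mediator result alone is not specific to that target. A target significant only in its single model may be a correlate of a working target or an upstream step in a chain, and should not be excluded on the joint model alone.
- Where scales are too collinear to separate, report a summed indirect effect for the group.
- Settle which targets are measured at T2 by reconciling sections 6.1 and 10.1.3.

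The cost is SAP wording and one extra model for each of the four outcomes, with no new data or participants. The joint model has less power for a weak true mediator (step 7), and it does not remove confounding by unmeasured factors.
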